#### Sampling trusts

The list for identifying trusts will be obtained from NHS Statistics monthly SitReps, which give details on monthly bed numbers and bed occupancy for critical care in NHS trusts in England. Where relevant, trusts have been combined to reflect mergers which have occurred since 2019.

Trusts by each age group will be randomly selected by region e.g. two trusts selected at random from the 17 in the East of England region to sample adult patients. This will be done by assigning each trust an ID number and using a random number generator to select unique IDs.

Where there are not enough trusts in a region to represent the population of that region (e.g. to power the PPS to detect 1% prevalence with a precision of 2% in paediatric patients, 3 trusts are required from East of England, which only has one trust with paediatric beds), additional trusts will be selected randomly from all regions.

Trusts which are not randomly selected, but which request participation, will be allowed to do so. Analyses will be run both including and excluding these participants.

#### Sampling patients

Patients in each included trust are to be selected at random by the NHS staff conducting the study. All patients should have an equal opportunity for selection regardless of their known or suspected infection or colonisation status. It is anticipated that collecting data on up to 20 patients will be manageable in the one-day survey period. Trusts with fewer than 20 ICU patients will be asked to include all of their patients, those with more will be asked to select a random sample of 20.

Trusts with more than one ICU for the relevant age group should sample patients at random from across all their units.

Guidance will be provided on how to randomly select patients, for example:

As first preference, and for an ICU with any number of beds:

 Use a random number generator to obtain a list of 20 bed numbers to sample e.g. https://www.random.org/

If a random number generator cannot be used:

For an ICU with approximately 40 patients:

- 1. Flip a coin to pick whether to start with bed 1 or 2
- 2. Sample every other bed

For an ICU with approximately 60 patients:

- 1. Draw lots to pick whether to start with bed 1, 2, or 3
- 2. Sample every third bed

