# Study design

A prospective, cluster randomised cross-sectional survey approach will be used to provide estimates of prevalence of CPE for clinically indicated samples and rectal screening (stool sample or rectal swab) isolates from the randomly selected acute trusts.

Samples taken for routine clinical management purposes from the selected patients (e.g. blood, urine, wound) will be included, as will rectal screening (stool sample or rectal swab) taken to determine if the patient is colonised with a CPE.

The selected patients receiving in-patient treatment in the participating trusts' units will be included in the survey on the survey date. A single survey day will be used for each trust to minimise the workload for the clinical teams and to optimise sample collection.

Intensive care ward staff will implement the survey by randomly selecting patients and providing relevant data for the survey. To ease the workload, an online survey tool will be used for data collection purposes. ICU staff will be advised on methods of randomly selecting patients within the ward; the method by which patients are selected will be dictated by the number of critical care beds.

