#### Laboratory specimen collection, transport and analysis

No additional samples – either clinical or screening – will be collected for this survey. Patients included who do not have a CPE result will be assumed to be negative.

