Indicate which carbapenemase family was detected (select all that apply)	Indicate which carbapenemase family was detected (select all that apply)	Multiselect drop-down
If Other, specify other carbapenemase family		Text
Screening (NB no additional sc	reening is required)	
*CPE on admission to Trust	Was the patient known to be CPE positive on admission to Trust	Single select drop-down: Yes – colonised Yes - infected No Unknown
*CPE screening on admission to Trust	Found to be CPE positive on admission to Trust.  "Yes" if screening specimen positive, "no" if screening specimen negative, "unknown" if no screen performed.	Single select drop-down: Yes No Unknown
*CPE on admission to ICU	Known to be CPE positive on this admission to ICU i.e. communicated/identified at time of admission.	Single select drop-down: Yes No Unknown
*ICU screen required	Did patient meet requirement to be screened for CPE on ICU in accordance with your policy?	Single select drop-down: Yes No Unknown
*ICU admission screen	Was patient screened for CPE on this admission to ICU?	Single select drop-down: Yes No Unknown

		1
*ICU admission screen date	Date admission screen was taken on ICU	DD-MM-YYYY
*Result of ICU admission screen	Indicate result from ICU CPE admission screen	Single select drop-down: Positive Negative Unknown
*Previous CPE	Indicate if patient known to be CPE colonised/infected in 12 months prior to first day of survey	Single select drop-down: Yes – colonised Yes - infected No Unknown
If previous history of CPE, specify date of most recent positive result.	Provide date of most recent CPE positive result (prior to ICU admission screen, if taken)	DD-MM-YYYY
Previous contact with CPE	Indicate if in contact with known CPE case during this admission	Single select drop-down: Yes No Unknown
Healthcare exposure		
*UK non-NHS hospital admission in previous 12 months	Any hospital admissions to non-NHS hospitals in the previous 12 months	Single select drop-down: Yes No Unknown
Specify UK non-NHS hospital admission	Provide name(s) of non- NHS hospitals admitted to in previous 12 months	Free text
*Healthcare overseas in previous 12 months	Any hospital admissions overseas in 12 months prior to admission at Trust	Single select drop-down: Yes No Unknown
Specify healthcare abroad	List countries where overseas healthcare received in previous 12 months	Multiselect dropdown of countries

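### Above the 20-patient cap, staff who can know CPE status make an unconcealed, unrecorded patient draw, so a redraw that moved known carriers in or out could not be detected

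*Protocol*

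**What the plan says.** Under Sampling patients the protocol states: "Patients in each included trust are to be selected at random by the NHS staff conducting the study". Study design gives the same people both tasks: "Intensive care ward staff will implement the survey by randomly selecting patients and providing relevant data for the survey". The safeguard is an instruction: "All patients should have an equal opportunity for selection regardless of their known or suspected infection or colonisation status". The Training section adds guidance on random selection.

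Selection arises only in larger trusts, because "Trusts with fewer than 20 ICU patients will be asked to include all of their patients"; those above the cap sample 20. The first preference is a random number generator run locally. If that cannot be used, the example for about 40 patients is "Flip a coin to pick whether to start with bed 1 or 2" and then every second bed. For about 60 patients it is "Draw lots to pick whether to start with bed 1, 2, or 3" and then every third bed.

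The outcome comes from results that already exist: "No additional samples – either clinical or screening – will be collected for this survey", and a patient without a CPE result counts as negative. Appendix 1 has a mandatory patient field described as "Known to be CPE positive on this admission to ICU i.e. communicated/identified at time of admission".

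Appendix 1 collects beds per trust and unit, and unit occupancy on the survey date. It has no field for the draw method, the starting bed, the numbers drawn, a patient's bed or the eligible patients not chosen. Trusts, by contrast, are selected by ID number and a random number generator (Sampling trusts).

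**The concern.** The person making the draw can already see most of what the survey will count. Because no sample is taken for the survey, a patient's recorded status largely exists before selection, apart from results still awaited. Choosing with that status in view is choosing on the outcome.

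The fallback makes this easy to act on. With fixed bed numbers there are only two or three possible samples, and staff can read off in advance which start includes a known carrier. The local generator has vastly more possible samples, but it too can be run again without trace. The survey team could check how many patients were sampled, but not whether they were the ones first drawn.

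At stake is the headline prevalence, mainly in adults. Few positives are expected, so a handful of moved carriers matters, and recruiting more trusts would not remove such a bias.

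**Working it through.** **1. The plan's own figure.** Adult option 3 (prevalence 1%, precision ±1%) is 767. With N = 4,090 beds, p = 0.01, d = 0.01, z = 1.96 and design effect 2:

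n = 2 × 4,090 × 0.0099 / [(0.01² / 1.96²) × 4,089 + 0.0099] = 80.98 / 0.1163 = 696.1, rounded up to 697; × 1.1 = 766.7, i.e. 767. The figure reproduces and is not affected by this point.

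**2. Expected adult sample.** Trusts needed under option 3 times mean capped occupancy (both in Sample size per region): 7×13 + 9×15 + 12×13 + 10×13 + 8×13 + 9×15 + 7×13 = 842 patients in 62 trusts.

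**3. Weight of one carrier.** At 1%, 842 × 0.01 = 8.4 expected positives. One carrier moved shifts the estimate by 100/842 = 0.12 points. With 767 patients it is 7.7 positives and 0.13 points.

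**4. What an unreported redraw buys under the fallback.** The chance of leaving out a given carrier rises from 1/2 to 1 − (1/2)² = 75% with a second coin flip. With a second drawing of lots it rises from 2/3 to 1 − (1/3)² = 89%.

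**5. How many adult trusts are above the cap.** The protocol does not say. Appendix 2 lists 133 adult trusts (14, 19, 23, 21, 23, 18 and 15 by region), against 135 in the Sample size table. Listed trusts times capped means: 14×13 + 19×15 + 23×13 + 21×13 + 23×13 + 18×15 + 15×13 = 1,803. Total occupancy is 3,305, so about 1,502 patients lie above the cap.

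- Lower bound: the largest trust has 142 occupied beds, 122 above the cap; 1,502/122 = 12.3, so roughly 12 trusts.
- Upper bound: the median is 14, so at most 67 of 135.

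With k such trusts, the 62 drawn contain about 62k/135 of them, supplying 20 × 62k/135 of the 842 patients: 13% at k = 12, 27% at k = 25, 60% at k = 55 and 73% at k = 67.

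**6. Shift in the adult estimate if staff in a share f of these trusts steer.** Assume 1% prevalence in every trust and every carrier known to staff.

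- *All carriers taken in.* Extra positives at f = 1 are (62/135) × 1,502 × 0.01 = 6.90, whatever k is. The shift is 6.90/842 = +0.82 points.
- *All carriers left out.* Positives lost at f = 1 are 0.20 × 62k/135, i.e. 2.30 at k = 25 and 5.05 at k = 55. The shift is −0.27 to −0.60 points.

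| f | taken in | left out, k = 25 to 55 | left out, k = 12 to 67 |
|---|---|---|---|
| 10% | +0.08 | −0.03 to −0.06 | −0.01 to −0.07 |
| 25% | +0.20 | −0.07 to −0.15 | −0.03 to −0.18 |
| 100% | +0.82 | −0.27 to −0.60 | −0.13 to −0.73 |

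For scale, the standard error at design effect 2 is √(2 × 0.0099/842) = 0.485 points. These are upper limits for the coin and lots, where a redraw can only swap between two or three fixed samples.

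**The case against.** The strongest reply is that the procedure as written is sound. Systematic sampling from a random start gives every bed the same chance, and a coin flipped once cannot be steered by someone who knows both results. Steering needs an unreported redraw against an explicit instruction, and the documents suggest no motive: a trust's line listing shows only its own data. The coin and lots are a fallback, offered as examples. Median occupancies of 14 (adult), 11 (paediatric) and 5 (neonatal) mean that most trusts take every patient. All of this stands, and it limits the point to large, mainly adult, trusts.

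The size is also modest unless steering is common. At f = 25% the shift is at most 0.20 points, one fifth of the precision target and about 0.4 of the standard error. At 1% prevalence many capped trusts would have no carrier to move. This stands too.

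What does not answer the point is the reliance on instruction and training. They neither conceal the draw nor leave a record. Nor can analysis repair it afterwards, because a draw that was not recorded cannot be checked.

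A practical objection is timing. The protocol is dated 7 April 2022, with training planned for March and the survey for April, so a change would come after training. That bears on the cost, not on the gap.

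**Conclusion.** The point holds as a weakness in procedure: in trusts above the cap, people who can know the outcome make an unconcealed draw that leaves no record. It is worth closing because the remedy is cheap. The protocol does not show that bias will occur. Each adult carrier moved is worth about 0.12 points. The plausible total depends on f, which nothing in the protocol informs, and on the number of capped trusts, which is known only to lie between roughly 12 and 67. The shifts also assume uniform 1% prevalence and that staff know every carrier.

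Three stronger readings are not supported:

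- A reader might infer that two or three possible samples make the fallback unfair. They do not; the exposure is the unrecorded redraw.
- A reader might infer that the risk-factor odds ratios are biased as well. Selection on CPE status alone leaves within-trust odds ratios unchanged, as in a case-control design. Bias needs selection that also depends on exposure, or pooling across trusts without allowing for trust.
- A reader might take the 1,502 patients above the cap (45% of 3,305) as the share of the sample at risk. They are the excess over the cap; the exposed share of the sample is somewhere from 13% to 73%.

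**What to change.** In Sampling patients, replace the ward-run draw and delete the coin and lots options:

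1. Staff number all eligible 8am patients across all units for the age group, in a fixed order such as unit and then bed.
2. They save or submit that numbered list and its total N before any random numbers are seen. Submitting N alone would not be enough, because patients could then be renumbered.
3. The survey team or the data capture system then releases a pre-generated random ordering for that trust and age group. Integers 1 to 200 would cover the largest adult trust (192 beds). The ordering must not be printed on, or sent with, the paper form ahead of numbering.
4. Staff take the first 20 numbers not exceeding N.
5. N and each sampled patient's list number are entered in the data capture system, and the numbered list is kept locally for checking.

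The cost is one prepared ordering per trust and age group, two data fields, an update to the training guide and the work of numbering patients before release. No extra patients or samples are needed and the sample size is unchanged. If the fields cannot be added in time, keeping the numbered 8am list and the numbers drawn would at least make the draw checkable.

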# Data collection

Data collection from patient records will be carried out by hospital staff, using a digital data collection system, adapted from the HCAI Data Capture System (DCS) used for ICCQIP and the mandatory surveillance of healthcare associated infections. Some additional data will be collected through linkage to Hospital Episodes Statistics. It is anticipated that the data collection will primarily be done by staff on the ward being surveyed, but it is also possible that infection prevention and control could also be brought in to assist with the survey process.

 Patients are recruited from a single day. However, there will be two weeks available following the study date for trusts to enter the data.

#### **Training**

For staff responsible for data collection, web-based training sessions will be provided by the PHE survey team prior to the survey. Training will include guidance on using the DCS, the random selection of patients for survey inclusion, and written user guides covering the DCS alongside this protocol.

#### Information collected

The survey will collect data on a number of broad topics. These include:

- Trust-level data
- ICU-level data
- Patient data
- Patient data (day of survey)
- Patient data (microbiology)

The majority of the survey will be filled in by ICU staff, but it is anticipated that some additional data not included in the survey can be provided via data linkage with other systems, including the Second Generation Surveillance System for microbiology results and Hospital Episodes Statistics for some patient data. All data that can be obtained via reliable data linkage has already been excluded from the Point Prevalence Survey questions. Data will be enriched using the NHS DBS.

Further details on the proposed questions to be included in the survey can be found in the appendix.

#### Data collection procedure

To minimise burden on clinical staff and to reduce time required for data analysis, it is proposed an online data collection system (DCS) will be used for this survey. This is already in use for ICCQIP. However, it is acknowledged that it may not be practical for staff to enter data directly while collecting data into the web-based tool, and therefore a printable version of the survey, which can be completed and data subsequently entered into the DCS, will be provided.

The HCAI/AMR team located at Colindale will provide the repository for the data and only key members of survey team will have access to that data, for all ICUs. A line listing report will be available for participating trusts to access and download their data; no data from other trusts will be available via the DCS.

#### Laboratory specimen collection, transport and analysis

No additional samples – either clinical or screening – will be collected for this survey. Patients included who do not have a CPE result will be assumed to be negative.

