#### **Methods**

# Aim and objectives

#### Aim

To generate an estimate of the prevalence of carbapenemase-producing *Enterobacterales* infections and colonisations among patients in intensive care units in England.

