#### **Assumptions**

- Prevalence is assumed to be below 3%, and likely closer to 0.5-1%
- A confidence of 95% will be used for all groups.
- The intra-cluster correlation is not known but is assumed to be relatively small. A
  design effect of 2 will be used to account for the cluster design.
- The sample size has been increased by 10% in all patient groups to allow for noncompletion of the survey.

Sample sizes for a range of prevalences and absolute precisions have been calculated for each age group. The prevalence and precision detectable are limited in some cases, especially in paediatrics, by the number of ICUs (e.g. the sample size required to detect 1% prevalence with absolute precision of 1% in the paediatric population is 379, greater than the number of ICU beds).

Option	Assumed prevalence	Absolute precision	Total number of patients required
Adult			
1	1%	+/- 2%	205
2	0.5%	+/- 1%	403
3	1%	+/- 1%	767
Paediatric	;		
1	0.5%	+/- 3%	44
2	0.5%	+/- 2%	93
3	1%	+/- 2%	162
Neonatal			
1	1%	+/- 2%	197
2	0.5%	+/- 1%	372
3	1%	+/- 1%	664

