#### The following data will be collected once per trust

Field name	Field description	Response
Trust code	Unique Trust code	System generated
*Reporting organisation	Trust name	Single select drop- down/system-filled
*Date survey commenced		DD-MM-YYYY
*What age groups are you submitting data on?		Multiselect drop-down: Adults Paediatrics
		Neonates
*Is there a CPE screening policy in operation at the trust?	Asked once per age group	Single select drop-down: Yes No
		Unknown
*What is the CPE screening policy at the trust?	Asked once per age group	Multiselect drop-down:  All admissions High-risk admissions High-risk areas Known CPE carriers Contacts of cases Other
If "other" screening policy, please specify	Provide details of screening policy in operation at Trust	Text
*Number of ICU beds	Number of ICU beds in the trust for the age range sampled	Integer
	Asked once per age group	

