Other admitted from	Specify if admitted from "other" location	Text

*Date admitted to ICU	Date admitted to ICU	DD-MM-YYYY
Time admitted to ICU	Specify time admitted to ICU	HH:MM (24-hour clock)
*Location admitted to ICU from	Setting patient admitted from into ICU	Single select drop-down: Home A&E HDU within same Trust Other ward within same Trust International transfer Nursing home Other Trust
		Non-NHS hospital Non-health-related institute Temporary accommodation Other Unknown
Other admitted from (ICU)	Specify if admitted to ICU from "other" location	Text
*If admitted to ICU from another ward within the same Trust, please specify	Specify specialty patient was admitted into the ICU from	Single select drop down Adult Paeds Neonates Other
If other, please specify	Specify other/specialty	Text
Please specify Adult speciality		
 
General medical
 
General surgical
 
Specialty
 
Intensive care
 

Please specify Paeds speciality		

Medical

Surgical

Specialty

Intensive care

		

Surgical

Specialty

	Γ	T
If 'Speciality', please specify which Paeds speciality	Specify other/specialty	Text
If 'Speciality', please specify which Neonatal speciality	Specify other/specialty	Text
APACHE II score	Score measures severity of disease for patients admitted to ICUs. Provide score assigned to patient on admission to ICU	Integer, ranging 0 - 71
Microbiology details		
*Was this patient tested for CPE, either as screening or as part of clinical investigations?		Single select drop-down: Yes No Unknown
*Was it a screening or clinical specimen?	Indicate if screening specimen or clinical specimen	Single select drop-down: Screening Clinical Unknown
*Date CPE specimen collected	Date specimen collected (if single specimen). If multiple specimens, please provide the most recent date.	DD-MM-YYYY
Specimen/laboratory number assigned to specimen		Free text
Indicate anatomical site specimen collected if clinical specimen		Single select drop-down
*Organism	Organism isolated associated with CPE positive result. If no result yet, select "Unknown/result awaited". If no organism isolated, select "No organism isolated".	Single select drop-down

	T	T
Does phenotypic testing indicate the presence of a carbapenemase?	Indicate if phenotypic (antibiotic susceptibility) testing indicates presence of a carbapenemase	Single select drop-down: Yes No Unknown

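### Counting every patient without a CPE result as negative biases patient-level prevalence downward by an amount that depends on testing coverage, and can confound comparisons and odds ratios

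*Protocol*

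**What the plan says.** The protocol section on laboratory specimen collection, transport and analysis has two sentences. The first is "No additional samples – either clinical or screening – will be collected for this survey". The second is "Patients included who do not have a CPE result will be assumed to be negative".

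The Aim is to estimate the prevalence of CPE "infections and colonisations among patients in intensive care units in England", a quantity defined over patients. The Data analysis section plans prevalence overall and by strata, and odds ratios for hypothesised risk factors. It does not qualify the rule.

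Appendix 1 treats testing as something that varies:
- The trust-level form asks "What is the CPE screening policy at the trust", with options from all admissions to high-risk admissions, known carriers or contacts. A trust may also report that it has no policy.
- The unit-level form asks how often the policy is followed, from almost never to almost always.
- The patient-level form asks "Was this patient tested for CPE, either as screening or as part of clinical investigations", with Yes, No and Unknown as answers.
- The organism field gives pending results their own code ("If no result yet, select" an unknown or awaited option).
- A separate field asks "Was the patient known to be CPE positive on admission to Trust".

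**The concern.** A patient who was never tested has an unknown CPE status. Calling that status negative is harmless only if no untested patient carries CPE. Otherwise positives are missed in proportion to the share left untested, and the loss varies with local policy and compliance.

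Two outputs are exposed. The first is the national patient-level prevalence, which the Background section wants as a baseline. The second is any comparison between groups tested at different rates, whether regions, ICU types, the inequalities named in the Objectives, or risk factors. In the risk-factor models the untested join the comparison group as CPE-negative. An exposure that makes screening more likely can then look associated with CPE when it is not. A larger sample does not remove this bias, and the confidence interval does not show it.

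**Working it through.** **The plan's own figure.** The sample sizes reproduce exactly from n = 2 × N × p(1−p) / [(d²/1.96²)(N−1) + p(1−p)], rounded up, then increased by 10% and rounded up. N is the number of beds and 2 is the design effect. For adults at p = 1% and d = 1%:
- The numerator is 2 × 4090 × 0.0099 = 80.98.
- The denominator is 0.0001/3.8416 × 4089 + 0.0099 = 0.1163.
- This gives n = 697, and 697 × 1.10 rounds up to 767, as stated.

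The arithmetic is sound, but it takes CPE status as known for every completed patient. The 10% allowance covers non-completion of the survey, not absence of a test.

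**Inputs for the effect of the rule.** The Assumptions section says "Prevalence is assumed to be below 3%, and likely closer to 0.5-1" per cent; 1% is used below. Coverage c (the share of sampled patients with a result) is not given, so 30% to 90% is assumed. RR is the prevalence in tested patients divided by that in untested patients, also assumed. A result, where present, is taken as correct.

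**Prevalence.** With true prevalence p:
- prevalence in the untested = p / (c × RR + 1 − c)
- prevalence in the tested = RR × that value
- reported under the rule = c × prevalence in the tested
- shortfall = (1 − c) × prevalence in the untested

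Example, c = 50% and RR = 3: untested 1% / (1.5 + 0.5) = 0.5%; tested 1.5%; reported 0.5 × 1.5% = 0.75%; shortfall 0.5 × 0.5% = 0.25 points.

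| Coverage | Rule, RR 1 | Rule, RR 3 | Tested-only, RR 3 | Rule, RR 10 | Tested-only, RR 10 |
|---|---|---|---|---|---|
| 90% | 0.90% | 0.96% | 1.07% | 0.99% | 1.10% |
| 70% | 0.70% | 0.88% | 1.25% | 0.96% | 1.37% |
| 50% | 0.50% | 0.75% | 1.50% | 0.91% | 1.82% |
| 30% | 0.30% | 0.56% | 1.88% | 0.81% | 2.70% |

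The truth is 1% in every row. At RR 1 the tested-only figure is 1% throughout. At RR above 1 the two figures lie on either side of the truth. At a true 0.5% and RR 1, the shortfall is half as large: 0.05 to 0.35 points instead of 0.1 to 0.7.

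**Odds ratios.** For an exposure with no true effect, coverage c1 in the exposed and c0 in the unexposed, and p = 1%, the apparent odds ratio is [p·c1/(1 − p·c1)] / [p·c0/(1 − p·c0)], close to c1/c0. For 90% against 30% it is (0.009/0.991) / (0.003/0.997) = 3.02. The same formula gives 2.01 for 80% against 40%, 1.50 for 90% against 60%, 1.40 for 70% against 50%, and 1.12 for 95% against 85%.

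**The case against.** The strongest counter-argument is that the obvious replacement, prevalence among tested patients, can be further from the truth. Suppose 40% are tested with prevalence 2% and 60% are untested with prevalence 0.5%. The truth is 0.4 × 2% + 0.6 × 0.5% = 1.1%. The rule gives 0.4 × 2% = 0.8%, which is 0.3 points low. The tested-only figure is 2.0%, which is 0.9 points high. This stands: tested-only should not become the sole headline. Models restricted to tested patients also select on testing, so they serve as a check and not as a replacement.

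Several stronger readings are tempting but not supported:
- *The rule contradicts the objectives on clinical and rectal screening isolates.* Those are proportions of isolates. An untested patient supplies none, so the rule leaves them unchanged. It bears on the patient-level aim.
- *Known carriers and patients with awaited results are recoded as negative.* The protocol does not say so. The form records known positivity and previous CPE, pending results have their own code, trusts have two weeks to enter data, and linkage to a microbiology system is anticipated. Only never-tested patients are clearly caught; the others need a stated rule.
- *Prevalence measures testing as much as CPE, and the odds ratios are driven by screening.* The first is literally so only if testing is unrelated to CPE. Coverage unrelated to an exposure leaves its odds ratio nearly unbiased.
- *Particular exposures, such as overseas healthcare, are known screening criteria.* The form lists policy options and names no such criterion.

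A SAP, not available here, could add coverage tables and sensitivity analyses, so their absence is not the point. The classification rule itself is fixed in the protocol.

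**Conclusion.** The concern holds for never-tested patients. If results are correct and any untested patient carries CPE, the bias in patient-level prevalence is downward. Its size is uncertain because the protocol gives no coverage. At 90% coverage the relative loss is about 1% to 10% across the scenarios tried. At 50% coverage and a true 1%, the reported figure is 0.5% if testing is unrelated to CPE and 0.75% at a threefold prevalence ratio. In absolute terms these shortfalls lie within the planned adult precision of 1 point, but they are large relative to a prevalence of 1%.

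Stratum comparisons and odds ratios can be confounded where coverage differs between the groups compared; the spurious odds ratio ran from 1.12 to 3.02 in the range tried. A reader might infer that regional differences or reported risk factors will simply reflect testing. Without coverage data the documents do not support that.

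**What to change.** In the laboratory specimen section, record never-tested patients as not tested instead of negative. State how awaited results, and known carriers without a new test, are classed.

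In the Data analysis section:
- Report the percentage tested overall, by stratum and by screening policy.
- Give prevalence with both denominators side by side, with neither as sole headline. Label the all-patient figure a lower bound, and label the tested-only figure as leaning high under targeted testing. Where testing is aimed at higher-risk patients the two bracket the truth, for example 0.75% and 1.50% around 1% at 50% coverage and threefold prevalence.
- Beside the all-patient risk-factor models, run the same models among tested patients, or weighted for the probability of testing, as a check.

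The form already collects tested status, whether a screen was required, screening policy and compliance, so no new field is needed. The cost is wording in two sections, extra tables and additional model runs. The tested-only figure will not have the planned precision: of 767 adults, about 537, 384 or 230 would be tested at 70%, 50% or 30% coverage. Having 767 tested would take 1,096, 1,534 or 2,557 sampled patients (767 divided by coverage). Its wider intervals should be accepted and stated.
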